
refractory pain conditions to widespread societal use for clinical pain.

2. **Objectives** (include all primary and secondary objectives)
 1. **Primary Aim 1: Evaluate the magnitude and duration of combined dronabinol and hydromorphone to reduce pain sensitivity in a validated model of pain.** We hypothesize that the addition of a dronabinol to hydromorphone will result in a dose-dependent increase in the magnitude and duration of analgesia in patients undergoing a validated laboratory model of pain.
 2. **Primary Aim 2: Evaluate the subjective responses to combinations of dronabinol and hydromorphone to determine the subjective, euphoric effects of the combination products.** We hypothesize that dronabinol will not increase the subjective ratings of positive drug effects or other proxy measures of abuse liability, relative to hydromorphone alone.
 3. **Primary Aim 3: Evaluate the degree to which combining dronabinol with hydromorphone impacts neurocognitive performance.** We hypothesize that dronabinol may reduce neurocognitive performance at high doses, relative to hydromorphone alone, though the degree to which this may occur is unknown. This aim is critical for the advancement of potential opioid/cannabinoid combination products.
 4. **Secondary Aim 1: Evaluate whether there are sex differences on study outcomes.** We hypothesize that dronabinol enhancement of hydromorphone-analgesia will be greater among female vs. male subjects.
3. **Background** (briefly describe pre-clinical and clinical data, current experience with procedures, drug or device, and any other relevant information to justify the research).

This study will systematically evaluate whether cannabinoids can enhance the analgesic efficacy of opioids, which will advance the use of cannabinoids for the treatment of acute and/or chronic pain.

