
Conclusion: This will be the 1st human laboratory study to evaluate combinations of cannabinoids and opioids on a comprehensive and validated quantitative sensory testing battery, and the results of this study will identify whether a signal for this medication combination exists that should be advanced into randomized controlled trial evaluations with clinical pain populations. This study will also assess aspects that would impact drug development (abuse liability, neurocognitive impairment) and the effect of participant sex on outcomes. The ultimate goal of this research will be to determine which medication/dose combinations may exert strong analgesic effects, while minimizing abuse liability and cognitive deficits, in order to advance these medications into clinical trials for the treatment of chronic pain. This is a logical first step towards evaluating combined cannabinoid/opioids treatments for chronic pain, and will provide data necessary to support numerous evaluations of combination treatments for this population.

4. Study Procedures

- a. Study design, including the sequence and timing of study procedures (distinguish research procedures from those that are part of routine care).

Project Overview: This study will enroll 100 healthy adults, and will aim to complete 60 (30 men, 30 women) participants. Participants will conduct a within-subject evaluation of the degree to which the FDA-approved cannabinoid dronabinol (Marinol) enhances the analgesic effect of the prototypic opioid hydromorphone (Dilaudid). Subjects will complete a Screening visit to establish study eligibility and 5 experimental sessions. Experimental sessions will occur approximately once weekly and will permit subjects to admit themselves into the clinical research unit the night before the session if interested. Subjects will be provided with taxi service to and from the session. Subjects will receive a dose of hydromorphone (4mg, oral) and a double-blind oral dose of study drug or placebo the

morning of each experimental session, and will undergo QST measures of laboratory evoked pain, provide self-report ratings of drug effects, and complete a neurocognitive battery. The order of sessions will be randomized with the exception of Session 1, which will always be active hydromorphone + placebo to ensure the participant has a safe response to hydromorphone before proceeding into the remaining sessions.

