Hydromorphone (Dialudid) is a potent mu-opioid agonist that we have extensive experience administering in controlled laboratory settings. Hydromorphone is not subject to differences in CYP metabolic enzymes (in contrast to other opioids such as oxycodone) and therefore will not require us to screen out individuals with recent exposure to CYP inhibitors/inducers, or to analyze/statistically control for CYP metabolic profiles. We have selected a 4mg oral hydromorphone dose for this study because we have data from another ongoing study (IRB00047423) indicating it produces a mild-moderate effect (versus a ceiling or floor effect) and will therefore allow us to visualize changes as a function of the dronabinol. 4mg oral hydromorphone is also a dose that is commercially available and regularly prescribed for analgesia, which increases the clinical relevance of this study. Based on clinical experience, we expect it to produce a moderate analgesic effect on pain. This is an important feature because too strong a dose could overwhelm the cannabinoid effect and prevent us from effectively evaluating the study hypotheses. A moderate dose of hydromorphone will better enable us to evaluate shifts in the analgesic curve as a function of the study drug, and provide a stronger assessment of whether cannabinoids will enhance the analgesic effect of hydromorphone.

Study Drug Dosing		
Condition	Hydromorphone Oral	Dronabinol Oral
Nonrandomized 1	4mg	Placebo
Randomized 2	4mg	2.5mg
3	4mg	5mg
4	4mg	10mg
5	placebo	placebo
Session 1 will be nonrandomized and used as a safety screening day. Sessions 2-5 will be randomized and counter-balanced across participants.		

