Demographic and drug use characteristics, including a positive signal (defined as >20 points rating from baseline on VAS rating of Drug Effect from Session 1), that are hypothesized a priori to be associated with outcomes (e.g., Body Mass Index) will be compared across sex groups and significant differences will be included as covariates in the subsequent analyses. All analyses will be repeated and sex (male/female) will be added as a factor to the analyses.

c. Statistical plan including sample size justification and interim data analysis:

Since this will be the first study to examine the effect of cannabinoids on opioid-induced analgesia using a within-subject laboratory model of pain, there are no data available upon which a power analysis may be directly based. Therefore, we have used G-power to estimate our sample size. We estimate that a within-subject comparison using peak change from baseline as the primary outcome measure and comparing 6 medication conditions will yield power of 0.95 to detect a main effect at even a low effect size (0.2) by enrolling a sample size of 45. For each study, we are proposing to enroll 60 subjects to ensure we will have 50 study completers, and we will enroll equal quantities of men and women to examine sex-based differences in responding. This approach will result in an overall completion sample of 50 per study, with subsamples of 25 per group, which is consistent with other within-subject evaluations of drug effects. This sample size has been powered to support within-subject effects of study drug and between-subject effects of sex on study outcome measures.

d. Early stopping rules.

The safety of participants is a priority of BPRU. The largest potential risk of this study is cardiovascular in nature. This notion is based upon the results of a published study that reported an increase in heart rate and blood pressure

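### The sex analysis selects its covariates by significance test and may adjust for a post-dose response to hydromorphone, so the overall sex difference is estimated with a bias of unknown direction

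*Combined protocol and SAP*

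**What the plan says.** Section 7b sets a two-step rule: candidates "will be compared across sex groups and significant differences will be included as covariates in the subsequent analyses". All analyses are then repeated with sex as a factor. Candidates are restricted to those "that are hypothesized a priori to be associated with outcomes (e.g., Body Mass Index"; besides BMI, the only one named is "a positive signal (defined as >20 points rating from baseline on VAS rating of Drug Effect from Session 1".

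Section 4a (Project Overview) describes "Session 1, which will always be active hydromorphone + placebo", and the dosing table in section 6a confirms that this condition is fixed: "Session 1 will be nonrandomized and used as a safety screening day". It is the only session with active hydromorphone and no dronabinol, so it is also the comparator for the three dronabinol doses.

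Secondary Aim 1 (section 2) is worded generally, "Evaluate whether there are sex differences on study outcomes", and then adds a directional hypothesis that dronabinol enhances hydromorphone analgesia more in women than in men. The protocol's opening summary justifies the sex analysis partly by citing known sex differences in opioid response. Section 7c says that the sample also supports "between-subject effects of sex on study outcome measures".

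The plan does not give a significance level for the screen, a full candidate list, a statement on whether covariates interact with drug condition, or an unadjusted companion analysis.

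**The concern.** There are two separate faults. First, a between-sex significance test decides which covariates enter, so the model that estimates the sex effect is not known until the data are seen. Second, the Session 1 signal is not a baseline characteristic. It is a response to study drug, and if men and women differ in opioid sensitivity it is one of the places where that difference shows. Adjusting for it changes the question from whether the sexes differ to whether they differ at a given level of opioid response. The screen makes that adjustment more likely the more the sexes differ on the signal. At stake is the overall sex difference on each study outcome, which is the general part of Secondary Aim 1.

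**Working it through.** **The plan's own figure.** Section 7c gives N = 45 for power 0.95 with effect size 0.2 and 6 conditions. Taking 0.2 as Cohen's f and assuming alpha 0.05, correlation 0.5 and sphericity, λ = f²·N·m/(1−ρ) = 0.04 × 45 × 6 / 0.5 = 21.6 on 5 and 220 df. That gives power 0.962, and N = 43 reaches 0.95. The figure is reproduced, but it concerns a within-subject main effect. The plan gives no figure for the sex effect, so what follows is illustration under assumed inputs.

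**Step 1: how often the screen admits the signal.** Two-proportion test at an assumed 0.05 level:

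| Signal rate by sex | Entry, 25 per sex (7c) | Entry, 30 per sex (4a) |
|---|---|---|
| 50% vs 70% | 0.30 | 0.35 |
| 50% vs 80% | 0.61 | 0.69 |
| 50% vs 90% | 0.90 | 0.94 |

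The screen also admits covariates by chance. With k independent candidates that do not differ by sex, the probability that at least one enters is 1 − 0.95^k, which is 23% for k = 5 and 40% for k = 10.

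**Step 2: what adjustment does to the sex effect.** In within-sex SD units, for a continuous covariate that is always included, adjusted effect = d_outcome − r × d_signal.

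- Signs aligned, both differences 0.7: 0.7 − 0.3 × 0.7 = 0.49; 0.7 − 0.5 × 0.7 = 0.35; 0.7 − 0.7 × 0.7 = 0.21.
- Signs opposed, r = 0.5: size 0.7 + 0.5 × 0.7 = 1.05.

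**Step 3: simulation of the rule as written.** The signal is dichotomised at about 50% prevalence and enters only if chi-square p < 0.05. The sex effect is estimated by least squares. True sex differences are 0.7 SD in outcome and in signal, with within-sex correlation r from 0.3 to 0.7.

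- Aligned: the signal enters in 54–58% of trials. When it does, the sex effect averages 0.57 (r = 0.3) down to 0.39 (r = 0.7); unadjusted, comparable trials give 0.75 to 0.81. Power falls from 0.68 to 0.54–0.39 with 25 per sex, and from about 0.76 to 0.61–0.47 with 30.
- Opposed, 25 per sex: when the signal enters, the effect averages 0.84, 0.93 and 1.02 in size for r = 0.3, 0.5 and 0.7. The chance of a significant sex effect under the rule rises from about 0.68 to 0.78, 0.85 and 0.91.

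A second data model, in which sex acts on outcome only through opioid sensitivity (0.8 SD shift, 25 per sex), gives a mean sex effect of 0.60 unadjusted, 0.36 if always adjusted and 0.43 under the rule, with power 0.60, 0.30 and 0.37. With a 0.5 SD shift the effects are 0.37, 0.22 and 0.29, and power is 0.28, 0.15 and 0.19.

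**Step 4: the sex-by-condition contrast.** In one balanced simulated data set, the three sex-by-condition terms were 0.100, 0.542 and 0.333. Adding the signal as a main effect moved the sex coefficient from 0.353 to −0.019 and left those three terms unchanged. Crossing the signal with condition changed them to −0.041, 0.484 and 0.175.

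**The case against.** The strongest reply is that the claim could easily be pushed too far, and on several counts that is right.

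- **Direction.** A reader might infer that the rule adjusts the sex difference away. That holds only if sex moves the signal and the outcome in line with their correlation. The opening summary says that the sexes differ in opioid response but not which way, and section 2 gives a direction only for dronabinol enhancement. With opposed signs the bias is away from zero.
- **Timing.** A reader might infer that the signal enters precisely when sex affects it. It does not: a true 0.7 SD difference brings it in only 54–58% of the time, and a null candidate enters about 5% of the time at an assumed 0.05 level.
- **Scope.** The directional hypothesis is a sex-by-condition contrast. With complete balanced data a main-effect covariate leaves it alone, and section 7b mentions no covariate-by-condition term.
- **Size.** The effect can be small. With signal prevalence near 85% and r = 0.3, entry drops to about 34% and power goes from 0.68 to 0.61. With only a 0.3 SD sex difference in the signal and r = 0.3, entry is 16% and power goes from 0.67 to 0.63. At r = 0.1 the mean effect under the rule is 0.66 against 0.69. The documents give no correlation between rated drug effect and the pain measures.
- **Candidate list.** Candidates must be hypothesized in advance, so this is not open-ended selection. Adjusting for a pre-dose trait such as BMI is partly a choice of estimand.

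All of this limits the consequence but does not rescue the rule. An advance expectation of association does not turn a post-dose response into a baseline covariate, and entry still depends on the observed data.

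**Conclusion.** The point holds in a bounded form. On the text it is firm that covariates for the sex analysis pass through a between-sex significance screen, and that a post-dose response from the hydromorphone-alone session is a named candidate. It follows that the adjustment set is data-dependent and that the overall sex difference can be biased by conditioning on a variable between sex and outcome.

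The documents determine neither the direction nor the amount. The simulated loss of power and the simulated inflation both rest on assumed effect sizes, correlations, prevalence and test level, and are illustrations only. The directional sex-by-dose hypothesis is at risk only if the covariate is crossed with condition, which the plan leaves open, or if data are incomplete. Because this affects a secondary aim and needs no new data, it should be corrected before analysis, but it does not threaten the primary within-subject comparisons.

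**What to change.** In section 7b:

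1. Replace the significance screen with a short fixed list of pre-dose covariates, for example age and BMI, included whatever the comparison between the sexes shows.
2. Take the Session 1 Drug Effect signal out of the main sex model. Report it by sex as a descriptive result, or in an analysis labelled as exploratory mediation.
3. Name the sex-by-condition contrast as the test of the directional hypothesis, and state whether any covariate is crossed with condition.

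The cost is a change of wording and a few degrees of freedom for the fixed covariates.

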Subject Recruitment: Subjects will be recruited from the greater Baltimore area using established recruiting resources and media advertising, including newspaper, radio, and website listings. We also have an extensive list of potential study volunteers who have given permission to call them regarding potential study participation. All interested individuals will first complete a phone screen to establish initial study eligibility and individuals who pass will be invited for an in-person screening during which final study eligibility will be determined.

Screening Visit: Subjects will complete a brief phone screen to determine initial eligibility and will be invited to complete an in-clinic screen. Subjects will review and sign an informed consent document with a study staff member to begin the Screening visit. Subjects will provide a urine sample that must test negative for illicit drugs and pregnancy (for females), and will then complete a battery of measures to establish study eligibility. Medical eligibility will be determined by medical staff and will consist of an ECG, a blood sample to analyze hepatic, hematologic, and chemistry functioning, and a medical history and physical, which will occur prior to any drug administration.

Experimental Sessions: Upon final eligibility confirmation, subjects will complete 5 experimental study sessions. The sessions will be conducted on a closed research unit and subjects will be permitted to stay the night before the session on a clinical research unit. We have chosen to not conduct the entire study using a continuous inpatient design because we want to impose a minimum 7-day wash-out period between opioid exposures so that any acute tolerance that may have developed to the hydromorphone dose has time to dissipate and so that dronabinol, which has an elimination half life of 19-36 hours, has sufficient time to be excreted between drug administrations.

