- **Primary Aim 1:** The primary outcome will be the area under the curve of each QST procedure, which will provide an assessment of the mean duration and magnitude of the drug effect. Primary outcomes will be tested with repeated two-factor (Drug Condition x Time) models to examine main and interaction effects for all raw data as designed. If there is large variation across subjects at the baseline timepoint, the raw data will be transformed as a change from baseline and analyzed in drug condition by time models. Statistical analyses will be conducted using multilevel analyses with an autoregressive covariance structure using SAS PROC MIXED Software¹³¹. These analyses will permit an examination for effects of drug condition and time effects associated within the course of the study. Interpretation of drug condition main effects and interactions will rely on Tukey post-hoc tests. This aim will also assess frequency of adverse events as a function of study drug.

Specific outcome variables for the QST procedures will be as follows:

- a. Heat Pain Threshold and Tolerance: HPT_h and HPT_o in °C (both in normal and capsaicin treated skin)
 - b. Pressure Pain Threshold: PPT_h in kilopascals
 - c. Thermal and Mechanical Temporal Summation: Verbal pain ratings (both in normal and capsaicin treated skin for MTS)
 - d. Conditioned Pain Modulation: The index score of CPM:PPT_h and CPM:TS (compared to baseline) for each dose
 - e. Cold Water Tolerance: Time to tolerance (compared to baseline) for each dose.
- **Primary Aim 2:** The Drug vs. Money questionnaire will be compared across dose conditions, using peak monetary rating for each dose as the primary outcome. Within-subject changes, as a function of dose, will be analyzed using a repeated measures analysis of variance (ANOVA).
 - **Primary Aim 3:** Neurocognitive tests will be compared as a function of study drug dose, using study session number (1-6) as a covariate to control for practice effects. Specific outcome measures will include:
 - a. Divided Attention Task (DAT): Accuracy with which they perform the two tasks
 - b. Digit Symbol Substitution Task (DSST): Accuracy, total number of patterns completed in allotted time
 - c. Computerized version of the Paced Auditory Serial Addition Task (PASAT): Summed of correct trials

b. Secondary outcome variables.

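### The power paragraph in section 7.c describes a different design; its 0.95 is not power for the dronabinol contrasts, and the claim of power for sex has no calculation

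*Combined protocol and SAP*

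**What the plan says.** Section 7.c holds the plan's only power figure: "comparing 6 medication conditions will yield power of 0.95 to detect a main effect at even a low effect size (0.2", with a sample of 45. The outcome is given as "using peak change from baseline as the primary outcome measure". It continues: "we are proposing to enroll 60 subjects to ensure we will have 50 study completers", that is, 25 completers per sex, and ends: "This sample size has been powered to support within-subject effects of study drug and between-subject effects of sex on study outcome measures".

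Other sections describe a different design:

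- **Conditions.** Section 4.a says "subjects will complete 5 experimental study sessions", and the dosing table in section 6.a lists five conditions: hydromorphone with dronabinol 0, 2.5, 5 or 10 mg, and double placebo. Section 7.a, Primary Aim 3, carries the same leftover as 7.c: "using study session number (1-6) as a covariate to control for practice effects".
- **Outcome.** Section 7.a, Primary Aim 1: "The primary outcome will be the area under the curve of each QST procedure".
- **Numbers.** The abstract gives 60 enrolled. The Project Overview in section 4.a gives 100 enrolled and 60 to complete.
- **Post-hoc tests.** Section 7.a, Primary Aim 1: "Interpretation of drug condition main effects and interactions will rely on Tukey post-hoc tests".
- **Hypotheses (section 2).** Aim 1 is that adding dronabinol to hydromorphone increases analgesia in a dose-dependent way. Secondary Aim 1 is that this enhancement is larger in women than in men.

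**The concern.** The mismatches in condition count, outcome and sample size suggest a paragraph carried over from another design. The more serious matter is which test the 0.95 belongs to. A main effect over all conditions can be driven wholly by hydromorphone against double placebo, which is not the Aim 1 question. Section 6.a expects the 4 mg hydromorphone dose to be moderately analgesic, so that contrast should supply part of the omnibus effect. A reader could take a null dronabinol result as coming from a trial with 95% power for dronabinol, and nothing in the plan would correct that.

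The sex sentence asserts power without an effect size, a power level or a calculation. It also names a between-subject effect, whereas the hypothesis is a sex-by-drug interaction.

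**Working it through.** **Inputs from the documents:** effect size 0.2, six conditions, N = 45, power 0.95 (7.c); five conditions (6.a); 50 completers (7.c) or 60 (4.a); Tukey tests (7.a).

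**Assumptions, because the documents are silent:** 0.2 is Cohen's f, alpha is 0.05, sphericity holds, and the between-condition correlation ρ is 0.5 (range 0.3 to 0.7). There is one summary value per person and condition, with differences in SD units.

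**1. The plan's own figure.** Noncentral F with λ = N·m·f²/(1−ρ) and df (m−1) and (N−1)(m−1). For m = 6, N = 45: λ = 45 × 6 × 0.04/0.5 = 21.6 and power is 0.962; 43 people suffice for 0.95. The figure reproduces.

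**2. The same test with five conditions.** N = 50: λ = 50 × 5 × 0.04/0.5 = 20, power 0.960 (0.865 at ρ = 0.3, 0.999 at ρ = 0.7). N = 60: λ = 24, power 0.985 (0.926 at ρ = 0.3). Reaching 0.95 takes 48 people. The wrong condition count alone does little harm.

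**3. Does f = 0.2 imply a dronabinol effect?** Take means (0, 0.5, 0.5, 0.5, 0.5), placebo first. The grand mean is 0.4 and the variance is (0.16 + 4 × 0.01)/5 = 0.04, so f = 0.20. Omnibus power is again 0.960 at N = 50, with every dronabinol contrast equal to zero.

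**4. Power for 10 mg against hydromorphone alone.** Let D be the 10 mg shift, with the lower doses proportional (0.25D and 0.5D), and let the hydromorphone-placebo shift be h × D. Holding f = 0.2 fixes D = 0.2/SD(0, h, h+0.25, h+0.5, h+1). The test is a noncentral t with SE = √(2(1−ρ)/N). Its critical value is the studentized range for five means divided by √2 (2.75).

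| h | D (SD) | N = 50, ρ = 0.5 | N = 50, ρ = 0.3 to 0.7 | N = 60, ρ = 0.5 |
|---|---|---|---|---|
| 0 | 0.2/0.374 = 0.53 | 0.85 | 0.67 to 0.98 | 0.92 |
| 0.5 | 0.2/0.500 = 0.40 | 0.53 | 0.36 to 0.81 | 0.64 |
| 1 | 0.2/0.663 = 0.30 | 0.27 | 0.17 to 0.50 | 0.34 |
| 2 | 0.2/1.030 = 0.19 | 0.09 | 0.06 to 0.17 | 0.11 |

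The Tukey difference detectable with 80% power is 0.51 SD at N = 50 (0.39 to 0.60 for ρ = 0.7 to 0.3) and 0.46 SD at N = 60 (0.36 to 0.55). For one planned contrast it is about 0.40 SD at N = 50 (0.31 to 0.47) and 0.37 SD at N = 60.

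**5. Sex main effect.** λ = N·m·f²/(1+(m−1)ρ). N = 50: 10/3 = 3.33, power 0.43 (0.36 to 0.55 for ρ = 0.7 to 0.3). N = 60: 12/3 = 4, power 0.50 (0.42 to 0.63). At ρ = 0.5, about 120 people are needed for 0.80 and 197 for 0.95. The f detectable with 80% power is 0.31 at N = 50 (0.27 to 0.35 for ρ = 0.3 to 0.7) and 0.29 at N = 60.

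**6. Sex-by-drug interaction.** The omnibus interaction uses the λ of step 2, giving 0.960 (N = 50) and 0.985 (N = 60). If the sexes do not differ in the two conditions without dronabinol, f = 0.2 means a sex difference in the 10 mg effect of 2 × 0.2/SD(pattern):

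- proportional to dose: 0.4/0.374 = 1.07 SD
- equal at all three doses: 0.4/0.490 = 0.82 SD
- at 10 mg only: 0.4/0.400 = 1.00 SD

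For a sex difference in one dronabinol contrast, a two-sample t test with 25 per sex has power 0.28, 0.41 and 0.79 at differences of 0.4, 0.5 and 0.8 SD.

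**The case against.** The strongest reply is that nothing was miscalculated. The 0.95 reproduces, five conditions with 50 or 60 completers still give 0.960 or 0.985, and choosing AUC over peak change cannot alter a result that depends only on a standardised effect. All of that stands; the fault is in applying the figure to this trial.

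Next, 7.c claims power only for a main effect, and an omnibus test followed by Tukey tests is the stated plan. If f = 0.2 held among the four hydromorphone conditions alone, power would be 0.927 (N = 50) or 0.966 (N = 60), falling to 0.809 or 0.882 at ρ = 0.3. But 7.c does not define the effect that way, and it gives no power for the contrast that Aim 1 rests on.

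On sex, the omnibus interaction does have 0.96 power at f = 0.2, so low power is not a feature of every sex test. That figure requires a sex difference of roughly 0.8 to 1.1 SD in the 10 mg effect, which is hard to square with the plan's description of 0.2 as low. The 120 and 197 concern a main effect that the protocol does not hypothesise; they bear only on the sentence as written.

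Finally, these calculations simplify the planned analysis, which is a condition-by-time mixed model with autoregressive covariance. The dose patterns are also assumed. Departure from sphericity lowers omnibus power: the plan's own case falls from 0.962 to 0.913 at epsilon 0.75 and 0.806 at epsilon 0.5. The figures illustrate size and are not exact replacements.

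**Conclusion.** The concern holds. The differences in condition count, outcome and sample size follow from the text alone, as does the absence of any sex calculation. That f = 0.2 is compatible with no dronabinol effect is exact arithmetic. The size of the shortfall is conditional on the assumptions listed: for 10 mg against hydromorphone alone, Tukey power lies anywhere from 0.06 to 0.98 with 50 completers, depending on the hydromorphone-placebo shift and the correlation. The stated 0.95 therefore says little about Aim 1. Power for a sex main effect at the stated effect size is about 0.4 to 0.6, not a level usually described as powered. This should be fixed, but it does not call the design into question.

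**What to change.** Rewrite section 7.c, with these changes:

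- State five conditions, the AUC outcome, alpha, the effect-size metric and the assumed correlation.
- Give one enrolment target and one completion target, and reconcile the abstract, section 4.a and section 7.c. The implied losses now differ: 10/60 = 16.7% against 40/100 = 40%.
- Correct the session range in section 7.a, Primary Aim 3, to match five sessions.
- If the omnibus figure is kept, say that it includes double placebo.
- Add the dronabinol-versus-hydromorphone difference detectable with 80% power: under Tukey about 0.51 SD (50 completers) or 0.46 SD (60); for a single planned contrast about 0.40 or 0.37 SD; each with its range over the correlation.
- Delete the claim of power for between-subject sex effects, or restate it as a detectable f of about 0.31 (50) or 0.29 (60) at 80% power. State separately what is claimed for the sex-by-drug interaction, with the effect given as a difference in SD.

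The cost is one rewritten paragraph and matching edits elsewhere. Enrolment and procedures need not change; the stated figures become less favourable.
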